13. ADVERSE EVENT REPORTING

13.1. Introduction

All observed or volunteered/spontaneously reported Adverse Events (AEs) regardless of treatment group or suspected causal relationship to the investigational product(s) will be reported as described in the following sections. For all AEs, the Investigator or medically qualified individual (MD/DO) must pursue and obtain information adequate both to determine the outcome of the AE and to assess whether it meets the criteria for classification as a Serious Adverse Event (SAE) requiring immediate notification (within 24 hours) to the Sponsor or its designated representative. For all AEs, sufficient information should be obtained by the Investigator or medically qualified individual to try to determine causality. The Investigator is required to assess causality. For AEs with a suspected causal relationship to the investigational product, follow-up by the Investigator or medically qualified individual is required until the event or its sequelae resolve or stabilize at a level acceptable to the Investigator, and the Sponsor concurs with that assessment.

13.2. Reporting Period

All AEs, whether serious or non-serious, observed or spontaneously reported, beginning from the time the informed consent is signed and dated, are collected on the source document. AEs of randomized subjects will be entered in EDC while screen failure subjects will not. Subject's participation in the clinical trial begins at signing the informed consent. All AEs are recorded even if the AE occurs prior to the subject's participating in any study-related procedure and/or receiving IP or investigational device. Nonserious AEs will be reported through the subject's last study visit (or termination if the subject terminates early from the study for any reason). Spontaneous reports of SAEs will be collected through and including 30 calendar days after administration of the subject's last dose or exposure to IP.

SAEs require immediate notification to the Sponsor or its designated representative. Any SAE occurring any time after the reporting period (30 calendar days post IP exposure or last dose) must be promptly reported if a causal relationship to study product is suspected.

13.3. Definition of an Adverse Event

An AE is any untoward medical occurrence in a subject after they have signed an informed consent for a trial involving an IP or medical device. Any AE that occurs after the signing of the informed consent, until first usage of IP, will be considered non-treatment emergent and cannot (by virtue of time of occurrence) have a causal relationship with the IP.

The event does not need to have a suspected causal relationship with the investigational product. An AE can therefore be any unfavorable and unintended sign, symptom, disease or injury temporally associated with the use of an investigational product, whether or not related to the investigational product. Examples of adverse events include, but are not limited to

- Abnormal test findings,
- Clinically important symptoms and signs,
- Changes in physical examination findings,
- Hypersensitivity, and
- Progression/worsening of underlying disease.

Additionally, they may include the signs or symptoms resulting from

- overdose,
- withdrawal,
- abuse,
- Drug misuse,
- Drug interactions,
- Medication errors,
- Investigational product dependency,
- Exposure *in utero*, and
- Study related procedure.

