13.9. Causality Assessment

The Investigator's or medically qualified individual (MD/DO) assessment of causality for investigational product (i.e., relationship to investigational product) must be provided for all AEs (serious and nonserious). An Investigator's causality assessment is the determination

of whether there exists a reasonable possibility that the investigational product caused or contributed to an AE.

- Not Related - An AE that is not related to the use of the drug
- Doubtful - An AE for which an alternative explanation is more likely, e.g., concomitant drug(s), concomitant disease(s), or the relationship in time suggests that a causal relationship to investigational product is unlikely.
- Possible - An AE that might be due to the use of the drug. An alternative explanation, e.g., concomitant drug(s), concomitant disease(s), is inconclusive. The relationship in time is reasonable; therefore, the causal relationship to investigational product cannot be excluded.
- Probable - An AE that might be due to the use of the drug. The relationship in time is suggestive (e.g., confirmed by dechallenge) and an alternative explanation is less likely, e.g., concomitant drug(s), concomitant disease(s).
- Very Likely - An AE that is listed as a possible adverse reaction and cannot be reasonably explained by an alternative explanation, e.g., concomitant drug(s), concomitant disease(s). The relationship in time is very suggestive (e.g., it is confirmed by dechallenge and rechallenge) for a causal relationship to the drug.

If the Investigator determines a SAE is associated with study procedures, the Investigator must record this suspected causal relationship in the source documents and CRF, as appropriate, and report such an assessment in accordance with the SAE reporting requirements, if applicable.

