6.5 SAFETY ANALYSIS

All subjects who received induced wounds will be included in the safety analysis. All adverse events reported during the adverse-event reporting period will be listed by subject number.

The number and percentage of subjects experiencing treatment-emergent adverse events will be presented by body system and preferred term. Treatment-emergent adverse events are those with a start date and time on or after the date and time of first use of investigational product, or the AEs start before the first use of investigational product and worsened after it. The latest version of the Medical Dictionary for Regulatory Activities (MedDRA) will be used as the adverse event classification system.

Number and percentage of subjects with serious adverse events will be summarised by MedDRA system organ class and preferred term.

Number and percentage of subjects with treatment-related adverse events will be summarized by MedDRA system organ class and preferred term. Treatment-related AEs are events evaluated by the investigator as possible, probable or very likely related to study medication. AEs with unknown relationship to treatment will be considered as treatment-related.

Number and percentage of subjects with serious adverse events will be summarized by MedDRA system organ class and preferred term.

APPENDICES

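### Protocol 13.3 and SAP 6.5 classify an adverse event that starts before the first bandage and then worsens in opposite ways, so it may be kept out of the treatment-related table if 13.3 is followed literally

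*Protocol*

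**What the plan says.** Protocol 13.3 (Definition of an Adverse Event) sets the rule for the period before the first bandage. An adverse event that arises in the interval from consent to first use of the product "will be considered non-treatment emergent and cannot (by virtue of time of occurrence) have a causal relationship with the IP". Nothing in the section deals with an event that starts in this period and becomes worse later.

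SAP 6.5 (Safety Analysis) defines treatment-emergent events in two parts. The first covers events that start at or after first use of the product. The second covers earlier events that get worse: "or the AEs start before the first use of investigational product and worsened after it".

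For the treatment-related table, SAP 6.5 says: "Treatment-related AEs are events evaluated by the investigator as possible, probable or very likely related to study medication". It then adds a default: "AEs with unknown relationship to treatment will be considered as treatment-related". Neither sentence refers to the time of onset.

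Protocol 13.9 (Causality Assessment) requires a causality assessment for every adverse event, serious or not. It describes that assessment as the determination "of whether there exists a reasonable possibility that the investigational product caused or contributed to an AE".

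The outputs concerned, in SAP Appendix 1, are Table 14.3.1 (treatment-emergent events) and Table 14.3.2 (treatment-related events).

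**The concern.** Aggravation of an existing skin reaction is a plausible harm of an adhesive bandage, and one of the four products is described in protocol Table 3 as medicated. An event of this kind can begin before any bandage is on. Adverse events are collected from consent, screening is 3 to 14 days before Day 0, and subjects use a supplied body wash during washout. On Day 0, section 11.2 lists wounding and the baseline assessments ahead of bandage placement.

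For such an event the two documents give different answers on emergence, and two sections of the protocol give different answers on causality. What is at stake is whether aggravation under a bandage reaches the treatment-related count through the investigator's judgement or is excluded by onset date. Product-related follow-up under protocol 13.1 depends on the same grade. Adverse events are the only safety assessment in SAP 4.3.

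**Working it through.** The plan gives no figure on this point, so the check sets the sections side by side and follows one event through them.

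**Test case.** An adverse event starts after consent and before the first bandage, and worsens once bandages are in use.

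**Emergence.**
- Protocol 13.3: not treatment-emergent, because onset precedes first use.
- SAP 6.5, second part of the definition: treatment-emergent, because it worsened after first use.

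These are opposite results for one event.

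**Causality.**
- Protocol 13.3: a relationship to the product is excluded by timing alone.
- Protocol 13.9: a grade is required, and contribution to the event counts. Aggravation is a form of contribution, so a grade of possible or higher is open to the investigator.

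No section says which of the two prevails.

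**How the worsening is recorded.** The documents do not say whether it continues the earlier record or is a new event. There are pointers to its being an event in its own right: 13.3 itself gives worsening of an underlying disease as an example of an adverse event, and 12.2 treats a finding at the screening examination as medical history only while it has not worsened. Neither is an instruction on how to record an event that began between consent and first use.

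**The three possible paths.**
1. One record, 13.3 applied literally. The event enters Table 14.3.1 through the SAP definition. It does not enter Table 14.3.2. The SAP default for unknown relationship does not help, because 13.3 supplies a definite answer.
2. One record, graded under 13.9. The event enters Table 14.3.1, and also Table 14.3.2 if graded possible or higher, or if the relationship is unknown.
3. Worsening entered as a new event with onset after first use. The 13.3 exclusion does not reach it. It enters Table 14.3.1, and Table 14.3.2 on the same grades as in path 2.

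Exclusion by rule occurs in path 1 only.

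**Weight of one subject.** Taking the planned number of about 35 as the safety set, 1/35 = 0.0286, or 2.9 percentage points of the treatment-related rate. This is the weight of any single subject. It does not estimate how many are affected, because the documents give no adverse event rates.

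**The case against.** The strongest reply is that the gap is real on paper but nearly empty in practice.

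- **Wounding route.** Under 12.2, expected reactions to tape stripping, healing and bandaging become adverse events only on exacerbation. If the exacerbation happens under the bandage, the adverse event itself starts after first use and 13.3 does not bar it. Section 11.8.2 also withholds test products from wounds that already show certain abnormal signs.
- **Washout route.** Section 11.2 has the back examined again on Day 0, several exclusion criteria concern skin conditions, 11.8.1 requires test sites clear of them, and under 13.2 events in screen failures are not entered in the database.
- **Causality.** Section 13.9 applies to all events, and nothing says that 13.3 overrides it.
- **Follow-up.** Section 11.7 separately requires it for events related to trial procedures.

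Most of this stands, and it makes such events few. It does not remove the conflict. The Day 0 examination is listed before wounding, so it cannot screen reactions to wounding. An event that does not exclude the subject can still be on record before the first bandage. The silence on whether 13.3 or 13.9 prevails leaves the outcome to the site's reading.

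A reader might go further and infer that bandage-aggravated events are systematically kept out of Table 14.3.2. The documents do not support that, since two of the three paths let them in. Nor is that table built from the investigator's positive grades alone, because events of unknown relationship are added. And an event that is treatment-emergent but not treatment-related is not an anomaly in itself, since the two tables answer different questions. The fault is that, on one path, onset date settles causality in place of the assessment that 13.9 requires.

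**Conclusion.** The contradiction holds: protocol 13.3 and SAP 6.5 disagree on emergence, and 13.3 and 13.9 disagree on causality, for an event that starts before first use and worsens after it. Loss from Table 14.3.2 is possible but conditional. It requires both that the worsening is kept under the original record and that the site lets 13.3 prevail over 13.9. Few events are likely to meet these conditions, and their number cannot be derived from the documents.

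This does not touch the efficacy analyses. The study is exploratory, and the SAP describes no between-product test of adverse events. The point still merits correction, because a stated rule misgrades an aggravated event when it is followed as written.

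**What to change.** Make three changes to protocol 13.3, consistent with SAP 6.5:

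1. Adopt the SAP definition of treatment-emergent, including the part on worsening after first use.
2. Limit the sentence that excludes a causal relationship to events that start before first use and do not worsen afterwards.
3. State that a worsening after first use is recorded with its own date, or as a new adverse event, and that the causality of the worsening is graded under 13.9. Choose one recording convention and give it in the case report form instructions.

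SAP 6.5 needs no change for this purpose. Moving the opening of the treatment-emergent window earlier, for instance to wounding, would not be enough: the causality exclusion would still apply to events that begin in washout.

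The cost is a sentence or two in the protocol and one date field on the adverse event page. The treatment-related count may come out slightly higher.

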13.4. Abnormal Test Findings

The criteria for determining whether an abnormal objective test finding should be reported as an adverse event are as follows:

- Test result is associated with accompanying symptoms, and/or
- Test result requires additional diagnostic testing or medical/surgical intervention beyond ordering a repeat test, and/or
- Test result leads to a discontinuation from the study, significant additional concomitant treatment, or other therapy, and/or
- Test result is considered to be an adverse event by the medically qualified Investigator or the Sponsor.

Merely repeating an abnormal test, in the absence of any of the above conditions, does not constitute an adverse event. Any abnormal test result that is determined to be an error does not require reporting as an adverse event.

13.5. Serious Adverse Events (SAE)

An AE or suspected adverse reaction is considered “serious” for a device study if, in the view of either the Investigator (physician) or the Sponsor, it results in any of the following outcomes:

- Results in death,
- Serious injury which means an injury or illness that:
 - Is life-threatening (immediate risk of death),
 - Results in permanent impairment of a body function or permanent damage to a body structure, or
 - Necessitates medical or surgical intervention to preclude permanent impairment of a body function or permanent damage to a body structure: permanent means irreversible impairment or damage to a body structure or function, excluding trivial impairment or damage
- Persistent or significant incapacity or substantial disruption of the ability to conduct normal life functions.
- A malfunction that the device (or similar device marketed by the same manufacturer or importer) would be likely to cause death or similar injury if the malfunction were to recur.
- Any suspected transmission of any infectious agent via a medicinal product (medically significant)

13.6. Hospitalization

Adverse events reported from clinical studies associated with hospitalization or prolonging hospitalization are considered serious. Any initial admission (even if less than 24 hours) to a healthcare facility meets these criteria. Admission also includes transfer within the hospital to an acute/intensive care unit (e.g., from the psychiatric wing to a medical floor, medical floor to a coronary care unit, neurological floor to a tuberculosis unit). Hospitalization does not include the following:

- Rehabilitation facilities,
- Hospice facilities,
- Respite care (e.g., caregiver relief),
- Skilled nursing facilities,
- Nursing homes,
- Emergency room visits (unless the reason for the emergency room visit meets one of the other outcomes in the definition of serious), and/or
- Same day surgeries (as outpatient/same day/ambulatory procedures)

Hospitalization or prolongation of hospitalization in the absence of a precipitating, clinical AE is not in itself a SAE. Examples include:

- Admission for treatment of a pre-existing condition not associated with the development of a new AE or with a worsening of the pre-existing condition (e.g., for work-up of persistent pre-treatment lab abnormality),
- Social admission (e.g., subject has no place to sleep),
- Administrative admission (e.g., for yearly physical exam),
- Protocol-specified admission during a clinical study (e.g., for a procedure required by the study protocol),
- Optional admission not associated with a precipitating clinical AE (e.g., or elective cosmetic surgery),

Pre-planned treatments or surgical procedures should be noted in the baseline documentation for the entire protocol and/or for the individual subject.

- Diagnostic and therapeutic non-invasive and invasive procedures, such as surgery, should not be reported as AEs. However, the medical condition for which the procedure was performed should be reported if it meets the definition of an AE. For example, an acute appendicitis that begins during the AE reporting period should be reported as the AE and the resulting appendectomy should be recorded as treatment of the AE.

13.7. Resolution

The Investigator will be required to assess the outcome of the AE for investigational product as one of the following:

- Resolved,
- Not Resolved,
- Fatal,
- Resolved with sequelae,
- Resolving, or
- Unknown (lost to follow up)

Any causally-related AEs unresolved upon completion of the last study visit will be followed up by the study staff until the event or its sequelae resolve or stabilize at a level acceptable to the Investigator and recorded on the CRF.

13.8. Severity Assessment

The severity of AEs will be assessed by the Investigator or medically qualified individual (MD/DO) using the following general categorical descriptors:

MILD:	Awareness of symptoms that are easily tolerated, causing minimal discomfort and not interfering with subject's usual function or normal everyday activities
MODERATE:	Sufficient discomfort is present to cause interference to some extent with subject's usual function or normal everyday activity
SEVERE:	Extreme distress, causing significant impairment of functioning or incapacitation; interferes significantly with subject's usual function; prevents normal everyday activities

Note the distinction between the severity and the seriousness of an AE. A severe event is not necessarily a serious event. For example, a headache may be severe (interferes significantly with subject's usual function) but would not be classified as serious unless it met one of the criteria for SAEs, listed above.

13.9. Causality Assessment

The Investigator's or medically qualified individual (MD/DO) assessment of causality for investigational product (i.e., relationship to investigational product) must be provided for all AEs (serious and nonserious). An Investigator's causality assessment is the determination

of whether there exists a reasonable possibility that the investigational product caused or contributed to an AE.

- Not Related - An AE that is not related to the use of the drug
- Doubtful - An AE for which an alternative explanation is more likely, e.g., concomitant drug(s), concomitant disease(s), or the relationship in time suggests that a causal relationship to investigational product is unlikely.
- Possible - An AE that might be due to the use of the drug. An alternative explanation, e.g., concomitant drug(s), concomitant disease(s), is inconclusive. The relationship in time is reasonable; therefore, the causal relationship to investigational product cannot be excluded.
- Probable - An AE that might be due to the use of the drug. The relationship in time is suggestive (e.g., confirmed by dechallenge) and an alternative explanation is less likely, e.g., concomitant drug(s), concomitant disease(s).
- Very Likely - An AE that is listed as a possible adverse reaction and cannot be reasonably explained by an alternative explanation, e.g., concomitant drug(s), concomitant disease(s). The relationship in time is very suggestive (e.g., it is confirmed by dechallenge and rechallenge) for a causal relationship to the drug.

If the Investigator determines a SAE is associated with study procedures, the Investigator must record this suspected causal relationship in the source documents and CRF, as appropriate, and report such an assessment in accordance with the SAE reporting requirements, if applicable.

13.10. Exposure In Utero (EIU)

For investigational products within clinical studies and for marketed products, an exposure *in utero* EIU occurs if

- a woman is exposed to the investigational product at any time between her last menses before conception through the delivery of the baby.
- there is a possibility of intrauterine exposure to drug via semen from the male partner who is taking the investigational product at the time of conception, thereby possibly exposing the fetus to the product.

If any study subject or study subject's partner becomes or is found to be pregnant during the study subject's participation, the Investigator must report the pregnancy to the Sponsor on a Pregnancy Notification Form (to be provided by the Sponsor when applicable). In addition, the Investigator must submit information regarding environmental exposure to a Sponsor product in a pregnant woman (e.g., a nurse reports that she is pregnant and has been exposed to a cytotoxic product by inhalation or spillage) using the Pregnancy Notification Form. This must be done irrespective of whether an adverse event has occurred and notification must

occur within 24 hours of awareness of the pregnancy. Initial notification via telephone to the Sponsor's study team contact must occur immediately upon the Investigator site's awareness of the pregnancy. The Pregnancy Notification Form must then be sent to the Sponsor within 24 hours of the site's awareness. The information submitted should include the anticipated date of delivery (see below for information related to induced termination of pregnancy).

Follow-up is conducted to obtain pregnancy outcome information on all EIU reports. The Investigator will follow the pregnancy until completion or until pregnancy termination (i.e., induced abortion) and then notify the Sponsor of the outcome. The Investigator will provide this information as a follow-up to the initial Drug Exposure During Pregnancy Collection Form A and/or End of Pregnancy Collection Form B (provided by the Sponsor when applicable). The reason(s) for an induced abortion should be specified. An EIU report is not created when an ectopic pregnancy report is received since this pregnancy is not usually viable. Rather, a SAE case is created with the event of ectopic pregnancy.

The Investigator should follow the procedures for reporting SAEs if the outcome of the pregnancy meets the criteria for immediate classification as a SAE (i.e., spontaneous abortion, stillbirth, neonatal death, or congenital anomaly [including that in an aborted fetus, stillbirth, or neonatal death]). In the case of a live birth, the "normality" of the newborn can be assessed at the time of birth (i.e., no minimum follow-up period of a presumably normal infant is required before an End of Pregnancy Collection Form B can be completed). The "normality" of an aborted fetus can be assessed by gross visual inspection, unless pre-abortion test findings are suggestive of a congenital anomaly.

Additional pregnancy outcomes that are classified as SAEs and should be reported as such include

- "Spontaneous abortion" includes miscarriage and missed abortion.
- All neonatal deaths that occur within 1 month of birth, without regard to causality.
- Any infant death after 1 month that the Investigator assesses as possibly related to in utero exposure to the investigational product.

